4. Health Economic Assessment: A within-RCT cost effectiveness analysis will be carried out based on the data collected in the trial. Resource use items in hospital and community care related to the treatment of venous ulceration or complications will be recorded for each patient at each follow-up. Resource use will be multiplied by UK unit costs obtained from published literature, HRG costs, and manufacturers' list prices to calculate overall costs. A standard tariff will be applied for each bandage change. Utilities (QALYs) will be calculated from the EQ-5D questionnaire administered to patients at baseline, 6 weeks, 6 months, 12 months and at one time point between October 2018 and March 2019. The extent of missing data will be assessed and appropriate methods to handle missing data will be applied if necessary. The incremental cost-effectiveness ratio will be calculated and compared to current UK decision making thresholds. Discounting will be applied at the standard rate. Sensitivity analysis will be carried out to test the robustness of results to alternative assumptions (for example, about missing data, or using per-protocol estimates of treatment effect) or alternative data (for example, about unit costs). Probabilistic sensitivity analysis will be carried out using bootstrapping. A decision model will also be constructed to take account of

outcomes (such as recurrence or healing) that might occur beyond time horizon of the RCT, or to take account of other relevant comparators in this patient group.

5. Other Markers of Clinical Success: The Venous Clinical Severity Score (VCSS) will be assessed at 6 weeks. In addition, the incidence of complications related to the endovenous intervention as well as the presence of residual / recurrent varicose veins will also be assessed at 6 weeks in the early arm.

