6.4 FOLLOW-UP ASSESSMENTS

Randomised patients will undergo routine leg ulcer care in community or hospital (or both) settings, in accordance with the local standard. This will equate to wound reviews and dressing changes ranging between once and 4 times per week (depending on the ulcer). The exact nature of dressings and date of dressing change will be documented by the completion of patient diaries. This will allow an accurate record of the dressing types used and will be collected and verified by the research nurse.

In addition, the following assessments will be conducted:

6.4.1 6-week clinic visit

- Clinical assessment
- In the compression plus early venous reflux ablation group, venous duplex scanning will be performed at 6 weeks post-randomization to verify anatomical treatment success. Depending on the results of the scan, the decision to perform further superficial venous interventions will be left to the discretion of the responsible clinical staff. Irrespective of the number and timing of venous interventions, all analyses will be performed on intention to treat.
- Wound tracing and photo
- Assessments of disease specific and generic quality of life (AVVQ, EQ5D & SF36) by means of self-completed questionnaire

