7.2 PLANNED ANALYSES

No formal interim analyses are planned. Informal interim analyses will be performed if requested by the Data Monitoring Committee (DMC) but findings will be made available to member of the DMC only. Basic descriptive methods will be used to present the data on study participants, trial conduct, clinical outcomes and safety (in total and for each study group separately). The primary outcome will be time to complete healing. We will test the hypothesis that there is no difference in time to complete healing between the control and intervention groups using a log-rank test

(two-tailed, 5% significance level). Kaplan-Meier survival curves will also be presented and we will perform a subsidiary analysis investigating the effect of study centre, participant age, ulcer size and chronicity on time to complete healing using Cox regression. To adjust for potential surgeon and centre effects, surgeon and centre will be included in the Cox regression analysis as random effects. All analyses will be on an intention-to-treat basis. If there is substantial cross-over, per-protocol analyses may be explored for sensitivity analyses. Safety and tolerability data will be presented by the two arms on an intention-to-treat basis. The statistical analysis plan (SAP) for the original trial (follow up to 1 year) will be finalised prior to the final analysis. An additional SAP for the extension follow-up (up to 5 years) will be finalised before the analysis of extension data.

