Appendix 1: Summary of assessments and follow-up visits

Time point	Estimated duration (mins)	Clinical evaluation*	Telephone follow-up**	Wound review/photo /tracing***	Collection of further endovenous intervention / duplex report	Venous duplex	Randomisation	Consent	Health Questionnaires (EQ-5D, SF-36, AVVQ)
Screening Visit	45	X				X		X ^a	
Baseline Visit	60-90	X		X***			X	X ^b	X
1 month	30		X						
6 weeks	60-90	X		X ^{?****}		X ^c			X
2 months	30		X	X [?]					
3 months	30		X	X [?]					
4 months	30		X	X [?]					
5 months	30		X	X [?]					
6 months	30		X	X [?]					X
7 months	30		X	X [?]					
8 months	30		X	X [?]					
9 months	30		X	X [?]					
10 months	30		X	X [?]					
11 months	30		X	X [?]					
12 months	30		X	X [?]					X
Extension follow-up Oct18 to Mar 19	240	X ^d	X		X			X ^e	X

*. Demographic details (age, sex, ethnicity), Pregnancy test for woman of child bearing potential. General clinical details (body mass index, ankle brachial pressure index – performed within previous 4 weeks, comorbidities, medication history). Ulcer details (duration, progression, previous ulcer history, size of current ulcer – using photography and planimetry). Details of venous disease (previous deep vein thrombosis, previous venous interventions, pattern of venous reflux on duplex)

. Ulcer healing assessment, compression type, AE assessment, Concomitant medications, health resource use. *tracing only performed at baseline & 6 weeks

a. Approached b Taken c. Only for those who have early endovenous treatment d. review of clinical notes only e. patients will not be reconsented as already consented for longer term follow-up at outset but will be asked if they wish to continue

?dependant on whether the ulcer has healed photo will be taken at verification visit and taken weekly for 4 weeks, unless otherwise confirmed by the trial manager. Once the ulcer has healed the patient will still be followed up with monthly phone calls.

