#### ***Secondary Outcomes***

- Ulcer Healing Rate: 24-week healing rate will be reported in addition to time to ulcer healing.
- Ulcer reoccurrence / Ulcer Free Time: Will be calculated up to 1 year for each study arm.
- Quality Of Life (QoL): Disease specific (AVVQ) and generic (EQ5D & SF36) quality of life assessments will be compared at 6 weeks post randomisation, 6 months and 12 months.
- Health Economic Assessment
- Other Markers of Clinical Success: The Venous Clinical Severity Score (VCSS) and will be assessed at 6 weeks. In addition, the incidence of complications related to the endovenous intervention as well as the presence of residual / recurrent varicose veins will also be assessed at 6 weeks.

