#### **4.8 Safety Data**

The safety data, including adverse events (AEs) and serious adverse events (SAEs) will be provided in a tabular format for the two arms (Table 11 and Table 12). AEs will be summarised by description and outcome and SAEs will be summarised by SAE reason, frequency, severity, and relationship to treatment, outcome and expectedness.

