EQ-5D health score			
Baseline			
6 weeks			
6 months			
12 months			
EQ-5D index value			
Baseline			
6 weeks			
6 months			
12 months			
SF-36 physical health			
Baseline			
6 weeks			
6 months			
12 months			
SF-36 mental health			
Baseline			
6 weeks			
6 months			
12 months			

\* Data presented as mean (SD) or median (IQR), as appropriate

Table 10 Summary of clinical success at 6 weeks after randomisation

	EVRA	Standard
	N=	N=
VCSS total score		
Yes		
No		

\* Data presented as frequency (percentage) for categorical variables

Table 11 Summary of adverse events

	EVRA	Standard
	N=	N=
No. surgical procedures		
Total number of AEs		
Description of AE		
Systemic		
Local		
Outcome		
Recovered		
Not yet recovered		
Death		
Unknown		
Missing		

\* Data presented as frequency (percentage) for categorical variables

Table 12 Summary of serious adverse events

	EVRA N=	Standard N=
No. surgical procedures		
Total number of SAEs		
Serious reason		
Death		
Life threatening		
Persistently disabling		
Hospitalisation required		
Congenital abnormality		
Other		
Frequency		
Single Episode		
Intermittent		
Frequent		
Continuous		
Unknown		
Severity		
Mild		
Moderate		
Severe		
Life threatening or disabling		
Relation to procedure		
Not related		
Unlikely		
Possible		
Probable		
Definite		
Outcome		
Recovered		
Not yet recovered		
Death		
Unknown		
Expectedness		
Expected		
Unexpected		

\* Data presented as frequency (percentage) for categorical variables

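### Complications are looked for more intensively after early ablation than after deferred ablation, and the SAP's by-arm adverse event tables make no allowance for it

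*Protocol*

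**What the plan says.** **Schedule.** Protocol 6.4.1 brings randomised patients in both arms to a 6-week clinic visit with clinical assessment, wound tracing and photograph, and quality-of-life questionnaires. One item is limited to the early arm, where "venous duplex scanning will be performed at 6 weeks post-randomization to verify anatomical treatment success". Appendix 1 repeats the limit in note c ("Only for those who have early endovenous treatment") and schedules no other duplex after screening.

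**Complications as an outcome.** Protocol 4.3.2, item 5, makes the incidence of endovenous complications a secondary outcome that "will also be assessed at 6 weeks in the early arm". The SAP's list of secondary outcomes (1.4) carries the same item without the arm limit: complications, "as well as the presence of residual / recurrent varicose veins will also be assessed at 6 weeks".

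**Deferred procedures.** Protocol 5.4 allows ablation in the standard arm once healing is confirmed, at 6 months, or on clinical deterioration. The follow-up that can pick up complications afterwards is the monthly call to month 12, which includes an adverse event assessment (Appendix 1, 8.4), the community notes or nurses (6.4.2), and the duty to report intervention-related events for 12 months (8.1, 8.3). None of these is limited by arm.

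**Reporting.** Protocol 7.2 says: "Safety and tolerability data will be presented by the two arms on an intention-to-treat basis". SAP 4.8 puts adverse and serious adverse events into tables by arm. Tables 11 and 12 both open with a row for "No. surgical procedures". Table 11 then gives the event total, a split into systemic and local events, and outcome. Neither table shows how an event was found.

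**The concern.** Protocol 8.2 lists deep vein thrombosis and superficial thrombophlebitis among the reportable events. A venous scan can show such an event in a patient without symptoms, and a telephone call cannot. If the true risk per procedure were the same in both arms, the early arm could still accumulate more recorded events because it has one more way of finding them.

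Tables 11 and 12 will be read as the safety cost of treating early, to be set against any gain in healing. With the procedure count as the top row, dividing events by procedures is the natural next step. Neither reading can separate a true excess from a product of the visit schedule. The primary outcome is not affected.

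**Working it through.** The plan gives no figure to reproduce here, so the check compares the schedule for the two kinds of procedure and then illustrates size under declared assumptions.

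**1. Follow-up after each kind of procedure**

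| | Early ablation | Deferred ablation |
|---|---|---|
| Timing | Within 2 weeks of randomisation | After confirmed healing, at 6 months, or on deterioration |
| Scheduled duplex | Week 6, so 4 to 6 weeks after an on-time procedure (6 − 2 to 6 − 0) | None |
| Scheduled complication assessment | Week 6 (protocol 4.3.2) | None tied to the procedure |
| Week-6 clinic visit | After the procedure | Usually before it |
| Calls, notes, reporting to month 12 | Yes | Yes, for the months that remain |

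The in-person healing verification visits (protocol 6.5) do not even this out. When ablation follows confirmed healing, the visits that confirm healing come before it. In the early arm they normally come after the procedure.

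**2. How many deferred procedures can precede week 6?** Input: 60% healed at 24 weeks in the standard arm (protocol 7.1, SAP 1.5). Assumption: constant hazard.
- Hazard = −ln(0.40)/24 = 0.0382 per week.
- Healed by week 6 = 1 − exp(−0.0382 × 6) = 20.5%.

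So about 80% would still be unhealed at week 6 and not yet eligible by the healing route. The documents give no rate for ablation on deterioration, which could come sooner. This step concerns timing only and does not measure bias.

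**3. Time under observation within 12 months.** After an on-time early procedure, about 50 to 52 weeks remain (52 − 2 to 52 − 0). After ablation at 6 months, about 26 remain (52 − 26). Raw events per procedure would therefore also compare unequal windows.

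**4. Size, illustration A: events seen only on the scan.** Early arm = 450/2 = 225. Assumptions: all are scanned, every finding is recorded as an adverse event, and no equivalent finding is made in the standard arm. Extra events = 225 × p, with p assumed.
- p = 0.5%: 1.1
- p = 1%: 2.3
- p = 2%: 4.5
- p = 3%: 6.8

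At p = 1%, the chance of at least one is 1 − 0.99^225 = 0.896.

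**5. Size, illustration B: incomplete detection after deferred procedures.** Assumptions: equal true risk per procedure, full detection in the early arm, and a fraction s detected after deferred procedures. The apparent early-to-standard ratio per procedure is 1/s.
- s = 50%: 2.00
- s = 75%: 1.33
- s = 90%: 1.11

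At an assumed 5% risk and 75% uptake of deferred ablation, the early arm records 225 × 0.05 = 11.25 events. The standard arm records 225 × 0.75 × 0.05 × s = 8.44 × s, which is 4.2, 6.3 or 7.6. Part of that per-patient gap is real exposure: even at s = 100% the standard arm has 8.44, because fewer procedures are done.

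**The case against.** The best reply is that the two arms differ only in intensity of follow-up, and that the table at issue is descriptive. Much of this stands.

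- A reader might infer that nobody looks for complications after deferred ablation, or that they would never be found. The documents do not support that. Calls, notes and the reporting duty apply to both arms, and deferred ablation follows each centre's usual practice (protocol 5.4), which may or may not include a scan.
- A reader might infer that the whole week-6 check is for the early arm only. The clinic visit and clinical assessment cover both arms. Only the duplex is restricted and, in the protocol though not in the SAP, the complication assessment.
- A reader might take the duplex for a thrombosis screen. Its stated purpose is anatomical success. Finding a thrombosis would be incidental, and nothing says that such a finding must be entered as an adverse event.
- SAP 4.8 names no test, Table 11 has no row for thrombosis, and no per-procedure rate is planned.

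The descriptive label does not dispose of the point. Complication incidence is a listed secondary outcome, SAP 2.5 says that secondary outcomes are tested at the two-sided 5% level, and SAP 4.7 gives no analysis of complications. Tables 11 and 12 are the only planned displays where it could appear. The SAP thus leaves a between-arm comparison open and attaches no caution about unequal ascertainment.

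There is also a fair objection to an over-strong remedy. Taking every week-6 finding out of the headline comparison would drop real early-arm harms, including those found at a clinic visit that both arms attend, and could tilt the result the other way.

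**Conclusion.** The point holds as a difference in how intensively complications are sought. After early ablation there is a scheduled duplex and, by the protocol, a scheduled complication assessment. After deferred ablation there is neither, and the by-arm tables do not allow for it. Any resulting bias would run against the early arm.

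The size cannot be derived from the documents. The figures of about 1 to 7 extra events, and of apparent ratios from 1.11 to 2.00, rest wholly on assumed silent-event and detection rates. They also assume that scan findings are recorded as adverse events and that centres do not scan as systematically after deferred procedures.

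A reader might go further and infer that any early-arm excess would be an artefact. That is not supported either: as planned, the table cannot tell an artefact from a true excess. The matter is worth correcting because a listed secondary outcome is affected and the remedy is cheap. It does not touch the primary result.

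**What to change.** 1. Reconcile protocol 4.3.2, item 5, with SAP 1.4 on whether the week-6 complication assessment is for the early arm only.
2. State in SAP 4.8 that procedure complications are ascertained differently in the two arms.
3. In Table 11, keep the all-events count by arm as the main display. Add a row for events found only on the scheduled week-6 duplex, excluding those found at the clinic assessment. Identify them from the adverse event record or, where that is silent, by querying the few thrombosis and thrombophlebitis events.
4. Show a supportive between-arm comparison without the duplex-only events.
5. If any per-procedure rate is reported, count events in the same fixed window after each procedure in both arms, with its length set in the SAP.

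The cost is some SAP wording, one table split and a few data queries. The documents describe no field for how an event was detected, and dates alone cannot show that an event was silent, so the route may stay uncertain for some events. Those should be reported as uncertain. No visit, scan or treatment changes.

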6.4.2 Further follow-up

- Assessments of disease specific and generic quality of life (AVVQ, EQ5D & SF36) by means of self-completed questionnaire at 6 months and 12 months post-randomization (sent to the patient).
- The research team will perform monthly telephone evaluation of the patient and access the community notes or telephone the community nurses in order to collect and verify the data collected.
- Once the research team has been informed that the ulcer has healed the patient will undergo an urgent verification visit

6.5 URGENT VERIFICATION VISIT

- A member of the local research team will perform the four verification visits to confirm healing. Photographs will be taken and send to the Trials Unit for independent verification. In order to minimise inconvenience to the participants, once core labs confirms healing it is not necessary for the research team to perform further verification visits. Please note all four photos should be taken unless the trial manager confirms otherwise.

6.6 LONGER TERM FOLLOW-UP

For each randomised patient a single telephone assessment will be performed between October 2018 and March 2019 to collect:

- Details of any further ulcer recurrence and healing events
- Assessment of ulcer related healthcare attendances and costs
- Details of all further venous interventions performed and any associated adverse events
- Assessments of disease specific and generic quality of life (AVVQ, EQ5D & SF36) by means of self-completed questionnaire completed over the telephone (or via post)

The research teams will also evaluate healthcare records to:

- verify ulcer recurrence and healing events
- obtain specific details about venous investigations and interventions performed including delays to intervention.

No anatomical assessments of long-term treatment success are planned; however, additional treatments will be recorded and included in the health-economic evaluations.

7. STATISTICS AND DATA ANALYSIS

Data and all appropriate documentation will be stored for a minimum of 10 years after the completion of the study, including the follow-up period in accordance with the Imperial College JCRO Archiving Study Documents SOP.

7.1 SAMPLE SIZE CALCULATION

The sample size calculation for this study was based on the primary outcome of ulcer healing. The ESCHAR trial was a similar randomised study, which published the final results in 2007 (see 1.1.3). A total of 500 patients with open or recently healed venous ulcers were randomised to standard therapy alone or standard therapy plus open surgery for superficial venous reflux. The study was powered and designed to evaluate differences in ulcer recurrence (rather than healing).

Consequently, the median time from randomization to treatment delivery was over 7 weeks. Nevertheless, the 24-week healing rate in patients randomised to standard treatment (compression alone) was approximately 60%. Two recent prospective studies evaluating the early treatment of superficial venous reflux suggested that the 24-week healing rate may be as high as 82%^{24 25}.

In order to calculate a sample size for this study, a benefit associated with early treatment is estimated at around 15%. Assuming the 24-week healing rate in the standard arm is 60%, to identify a difference in 24-week healing rates of 15% between the two groups (60% vs 75%) with 90% power and allowing for 10% dropout the study will therefore require 416 subjects (208 in each arm, 254 healed leg ulcers in total). To incorporate further allowances for protocol violations and unexpected dropouts, the target sample size will be 450 patients.

Assuming a 15% drop out rate for the study and that 90% of primary ulcers eventually heal, it is estimated that >340 of the recruited 450 patients will be eligible for inclusion in the ulcer recurrence analysis. With this number of participants, and allowing for the healing rates (of the index ulcer prior to entry into this analysis of ulcer recurrence) to differ by up to 20% between the two study arms, the study extension will have at least 80% power to detect a difference of 15% or more in ulcer recurrence rates between the two arms at the 5% significance level.

7.2 PLANNED ANALYSES

No formal interim analyses are planned. Informal interim analyses will be performed if requested by the Data Monitoring Committee (DMC) but findings will be made available to member of the DMC only. Basic descriptive methods will be used to present the data on study participants, trial conduct, clinical outcomes and safety (in total and for each study group separately). The primary outcome will be time to complete healing. We will test the hypothesis that there is no difference in time to complete healing between the control and intervention groups using a log-rank test

(two-tailed, 5% significance level). Kaplan-Meier survival curves will also be presented and we will perform a subsidiary analysis investigating the effect of study centre, participant age, ulcer size and chronicity on time to complete healing using Cox regression. To adjust for potential surgeon and centre effects, surgeon and centre will be included in the Cox regression analysis as random effects. All analyses will be on an intention-to-treat basis. If there is substantial cross-over, per-protocol analyses may be explored for sensitivity analyses. Safety and tolerability data will be presented by the two arms on an intention-to-treat basis. The statistical analysis plan (SAP) for the original trial (follow up to 1 year) will be finalised prior to the final analysis. An additional SAP for the extension follow-up (up to 5 years) will be finalised before the analysis of extension data.

